3.9 Subgroup and Multivariate Analyses

Supportive analyses will be performed to determine whether the estimated treatment effect that is observed for the primary analysis of PFS is consistent across selected subgroups of patients. The HR (or odds ratio) for treatment effect will be estimated within each subgroup. If a subgroup consists of fewer than 10% of Phase 2 randomized patients, analysis within that subgroup will be omitted. Forest plots will be used to display the HRs and 95% CIs across subgroups. Kaplan-Meier figures may be provided for each treatment arm within each subgroup.

The results of the subgroup analyses will be ordered according to the hierarchy listed below (Tier 1 and Tier 2). The hierarchy was determined according to the baseline factor's relative prognostic importance for patients with advanced epithelial ovarian cancer. Tier 1 represents the subset of baseline factors with the greatest anticipated prognostic importance, etc.

Tier 1 subgroup analyses:

- Presence of bulky disease (defined as presence of a tumor ≥ 50 mm) (yes vs. no)
- Platinum based therapy (resistant, refractory and sensitive)
- History of progression while on primary platinum treatment or within 1 month from completion of primary platinum-containing regimen versus not
- Number of prior platinum-based therapies (< 2 , ≥ 2)
- Disease stage at initial diagnosis (stage II, stage III/locally advanced, stage IV)
- [REDACTED]
- [REDACTED]

Tier 2 subgroup analyses:

- Prior anti-cancer therapies
- Prior therapy for advanced disease (yes, no)

- Prior adjuvant/neoadjuvant therapy (yes, no)
- Prior chemotherapy (yes, no)
- Prior radiation therapy (yes, no)
- Race (Caucasian, all others)
- Age group at initial diagnosis (< 65, \geq 65 years)
- Age group at study entry (< 65, \geq 65 years)
- ECOG performance status at study entry (0, 1)
- Body mass index (BMI) at study entry (< 30, \geq 30)

3.10 Safety Analysis

Safety analyses will be performed on the Safety Analysis Set.

3.10.1 Adverse Events

An AE is defined as any untoward medical occurrence in a patient or clinical investigation patient administered a pharmaceutical product, and that does not necessarily have a causal relationship with this treatment. An AE can therefore be any unfavorable and unintended sign (including an abnormal laboratory finding), symptom, or disease, temporally associated with the use of a medicinal (investigational) product, whether or not the AE is related to the medicinal (investigational) product. The term also covers laboratory findings or results of other diagnostic procedures that are considered to be clinically relevant as determined by the Investigator.

Analyses of AEs will be based on the principle of treatment emergence. Treatment-emergent AEs are defined as having onset after study drug dosing or a sign, symptom, or diagnosis that worsens after study drug dosing. Henceforth, whenever an analysis or summary of AEs is mentioned, it is intended that this is in reference to TEAEs, unless it is stated otherwise.

If AE start dates are completely missing or partially missing, the date imputation rules described previously in [Section 3.1.4](#) will be applied for the determination of treatment-emergence. This algorithm will be used only if the end date of the AE (if reported) indicates the event was not resolved before the first administration of study drug. Imputed AE dates will not be used to calculate the duration of AE episodes.

All AEs will be coded according to System Organ Class (SOC) and Preferred Term

(PT) using the Medical Dictionary for Regulatory Activities (MedDRA) dictionary (Version 19.0 or later).

For the escalation phase, the observed DLT rate in each dose cohort will be calculated by the crude proportion of patients who experienced DLT with a 2-sided, 95% exact binomial CI.

A summary of AEs, including incidences of:

- AEs
- SAEs
- AEs related to entinostat (“possibly related” or “related”)
- AEs related to avelumab (“possibly related” or “related”)
- AEs related to any study drug
- SAEs related to entinostat, avelumab, or both
- AEs leading to dose modification of entinostat, avelumab, or both
- AEs leading to discontinuation of entinostat, avelumab, or both
- AEs with a fatal outcome
- AEs with a CTCAE severity grade of Grade 3 or greater
- AEs with CTCAE severity of Grade 3 or greater related to entinostat, avelumab, or both

will be presented by dose cohort in Phase 1 and by treatment arm in Phase 2.

Incidences of all AEs will be presented by SOC and PT by dose cohort in Phase 1 and by treatment arm in Phase 2. SOCs will be sorted alphabetically. Within an SOC, PTs will be presented by decreasing incidence overall. Incidences of SAEs, and incidence of related SAEs by PT only, will be presented by decreasing incidence overall.

Incidence of AEs will also be presented by PT and severity, and by PT and relationship to study drug. Incidence of AEs of Grade 3 or greater, and incidence of related AEs of Grade 3 or greater, will also be presented by PT. For patients experiencing the same PT at multiple severities, the occurrence of the AEs with the greatest severity will be used in the analysis of incidence by severity. For patients experiencing the same PT at multiple relationship levels, the occurrence of the AEs with the strongest relationship to study drug will be used in the analysis of incidence by relationship to study drug.

All reported AEs, regardless of whether they were treatment-emergent, will be included in patient listings. Listings of all SAEs and AEs leading to discontinuation of entinostat, avelumab, or both will also be provided.

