2.3.1 Number of Patients and Sample Size Considerations

Phase 1b/Safety Lead-in (Dose Determination Phase):

Up to 18 patients evaluable for safety are expected to be enrolled in the Safety Lead-In/Dose Determination Phase of the study, which employs a rolling 6 Phase 1 trial design ([Skolnik 2008](#)). Two to 6 patients can be concurrently enrolled into a dose level, dependent upon: (1) the number of patients enrolled at the current dose level; (2) the number of patients who have experienced DLT at the current dose level; and (3) the number of patients entered but with tolerability data pending at the current dose

level. Accrual is suspended when a cohort of 6 has enrolled or when the study endpoints have been met.

For example, when 3 participants are enrolled onto a dose cohort, if toxicity data are available for all 3 when the 4th participant entered and there are no DLTs, the 4th participant is enrolled. If data are not yet available for 1 or more of the first 3 participants and no DLT has been observed, or if 1 DLT has been observed, the new participant is entered at the same dose level. Lastly, if 2 or more DLTs have been observed, the dose level is de-escalated. This process is repeated for participants 5 and 6. In place of suspending accrual after every 3 participants, accrual is only suspended when a cohort of 6 is filled. A participant who is unevaluable for toxicity will be replaced with the next available participant if de-escalation rules have not been fulfilled at the time the next available participant is enrolled onto the study. Therefore, between 6 and 18 patients will be included in the Phase 1b/Safety Lead-in (Dose Determination) component.

NOTE: patients who discontinue the study for reasons other than study drug-related toxicities before completing Cycle 2 will be replaced.

Phase 2/Expansion Phase:

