3.2.3 Safety Analysis Set

Without otherwise specified, the Safety Analysis Set will be used for the analysis of safety data in both the Phase 1b and Phase 2 portions of the study. The Safety Analysis Set will include all patients who received at least one dose of either study drug, entinostat, or avelumab. Patients will be included in the treatment group corresponding to the study drug they actually received. For most patients this will be the treatment group to which they were randomized. Patients who took incorrect study drug for the entire treatment period will be included in the treatment group corresponding to the study drug they actually received. At least one laboratory or vital sign measurement obtained, subsequent to at least one dose of study treatment, is required for inclusion in the analysis of a safety specific parameter. To assess change from baseline, a baseline measurement is also required.

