Table 14.3.5G	[REDACTED]
Table 14.3.5H	[REDACTED]
Table 14.3.5I	PFS by prior therapy for advance disease (yes vs. no) – Phase 2 (FAS)
Table 14.3.5J	PFS by prior adjuvant/neoadjuvant therapy (yes, no) – Phase 2 (FAS)
Table 14.3.5K	PFS by prior chemotherapy (yes, no) – Phase 2 (FAS)
Table 14.3.5L	PFS by prior radiation therapy (yes, no) – Phase 2 (FAS)
Table 14.3.5M	PFS by race (Caucasian, all others) – Phase 2 (FAS)
Table 14.3.5N	PFS by age group at initial diagnosis (<65, ≥ 65 years) – Phase 2 (FAS)
Table 14.3.5O	PFS by age group at study entry (<65, ≥ 65 years) – Phase 2 (FAS)
Table 14.3.5P	PFS by ECOG performance status at study entry (0, 1) – Phase 2 (FAS)

Table 14.3.5Q	PFS by BMI at study entry (<30, \geq 30) – Phase 2 (FAS)
Table 14.3.6	Non-Protocol Anti-Cancer Therapy/Interventions – Phase 2 (FAS)
Table 14.3.7A	Objective Response Rate (RECIST 1.1) – Phase 2 (FAS)
Table 14.3.7B	Objective Response Rate (irRECIST) – Phase 2 (FAS)
Table 14.3.8A	Clinical Benefit Rate (RECIST 1.1) – Phase 2 (FAS)
Table 14.3.8B	Clinical Benefit Rate (irRECIST) – Phase 2 (FAS)
Table 14.3.9	Duration of Response – Phase 2 (FAS)
Table 14.3.10	Time to Response – Phase 2 (FAS)
Table 14.3.11	Overall Survival – Phase 2 (FAS)
Table 14.4.1	Overall Treatment-Emergent Adverse Event Information - Phase 2 (Safety)
Table 14.4.1.1	Dose Limiting Toxicities – Phase 1b (Safety)
Table 14.4.1.2	Treatment-Emergent Adverse Events by System Organ Class and Preferred Term -Phase 1b (Safety)
Table 14.4.2	Treatment-Emergent Adverse Events by System Organ Class and Preferred Term - Phase 2 (Safety)
Table 14.4.3	Treatment-Emergent Adverse Events by Preferred Term and Maximum Severity – Phase 2 (Safety)
Table 14.4.4.1	Treatment-Emergent Adverse Events by Preferred Term and Relationship to Any Study Drug – Phase 2 (Safety)

Table 14.4.4.2	Treatment-Emergent Adverse Events by Preferred Term and Relationship to Entinostat Alone – Phase 2 (Safety)
Table 14.4.4.3	Treatment-Emergent Adverse Events by Preferred Term and Relationship to Avelumab Alone – Phase 2 (Safety)
Table 14.4.5.1	Treatment-Emergent Adverse Events with Severity of Grade 3 or Greater – Phase 2 (Safety)
Table 14.4.5.2	Treatment-Emergent Adverse Events with Severity of Grade 3 or Greater and Judged Related to Any Study Drug – Phase 2 (Safety)
Table 14.4.5.2.1	Treatment-Emergent Adverse Events with Severity of Grade 3 or Greater and Judged Related to Any Study Drug – Phase 1b

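### The SAP places the Phase 1b DLT rate on all dosed patients, so any dosed patient who was replaced dilutes the rate and its exact CI

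*SAP*

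**What the plan says.** SAP Section 3.10.1 gives the estimator for the lead-in: "the observed DLT rate in each dose cohort will be calculated by the crude proportion of patients who experienced DLT", reported "with a 2-sided, 95% exact binomial CI". That sentence names neither an analysis set nor an evaluability condition.

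Three other places supply the set:

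- Section 3.10, the parent section: "Safety analyses will be performed on the Safety Analysis Set".
- Section 3.2.3, as the default for both phases: "the Safety Analysis Set will be used for the analysis of safety data in both the Phase 1b and Phase 2 portions of the study". Membership is wide: "The Safety Analysis Set will include all patients who received at least one dose of either study drug, entinostat, or avelumab".
- Section 6.1, where the title of Table 14.4.1.1 reads "Dose Limiting Toxicities – Phase 1b (Safety" (closing bracket omitted here).

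Section 3.3.3 lists DLT determination among the safety variables, so the default applies to it. Section 3.2 defines four sets (Full, Per-Protocol, Safety and PK), and none depends on being evaluable for DLT.

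Section 2.3.1 handles the same patients differently. It replaces a participant who is unevaluable for toxicity, provided the de-escalation rules have not already been met, and it adds that "patients who discontinue the study for reasons other than study drug-related toxicities before completing Cycle 2 will be replaced".

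**The concern.** The design and the analysis treat the same patients in opposite ways. Section 2.3.1 regards a patient who leaves early without toxicity as giving too little information about DLT, and fills the place with another patient. The analysis then keeps that patient, if dosed, in the denominator of the DLT proportion. Someone who was not followed long enough to show a DLT is counted as having been followed and found free of one.

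The error can run in one direction only: a lower reported rate and lower confidence limits. Determining DLTs and the MTD or RP2D is the Phase 1b primary objective (Section 2.1.1), so this is the main numerical summary from that part of the trial. A reader of the study report would take it to describe the patients whom the design counts as evaluable.

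**Working it through.** **Inputs**

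- Full cohort: 6 patients (Section 2.3.1).
- Dose levels: three, namely the starting level and two lower ones (Section 2.3.4).
- Interval: two-sided 95% exact binomial (Section 3.10.1), taken as Clopper-Pearson.
- u = replaced patients in a cohort who had received at least one dose. The SAP gives no figure; u = 0 to 3 is assumed.

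**The plan's own figure.** The SAP states no DLT rate or interval. The related figure that it does state is the Phase 1b maximum of 18 patients evaluable for safety: 3 levels x 6 = 18, which reproduces. That maximum therefore equals full cohorts of 6 with no room for replaced patients, whereas the Safety Analysis Set would add any replaced patient who was dosed.

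**Formulae.** With x DLTs:

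- rate on evaluable patients = x/6
- rate on the Safety Analysis Set = x/(6+u)
- ratio of the second to the first = 6/(6+u)
- lower limit = Beta quantile at 0.025 with parameters x and n-x+1 (0 if x = 0)
- upper limit = Beta quantile at 0.975 with parameters x+1 and n-x

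The ratio is 6/7 = 0.86, 6/8 = 0.75 and 6/9 = 0.67 for u = 1, 2 and 3.

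| DLTs | n = 6 (u = 0) | n = 7 (u = 1) | n = 8 (u = 2) | n = 9 (u = 3) |
|---|---|---|---|---|
| 0 | 0% (0-45.9%) | 0% (0-41.0%) | 0% (0-36.9%) | 0% (0-33.6%) |
| 1 | 16.7% (0.4-64.1%) | 14.3% (0.4-57.9%) | 12.5% (0.3-52.7%) | 11.1% (0.3-48.2%) |
| 2 | 33.3% (4.3-77.7%) | 28.6% (3.7-71.0%) | 25.0% (3.2-65.1%) | 22.2% (2.8-60.0%) |

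**Expected value.** Take an illustrative true DLT probability of 0.33 among evaluable patients, with replaced patients contributing no DLT. The expected reported rate is 0.33 x 6/(6+u) = 0.283, 0.248 and 0.220 for u = 1, 2 and 3.

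**Coverage of the interval.** Computed over the 6 evaluable patients with the enlarged denominator, coverage stays at or above 98.3% for true probabilities of 0.20 and 0.33 at every u from 0 to 3. Of the cases examined (0.20, 0.33 and 0.50), it falls below 95% only at 0.50 with u = 3, where it is 89.1%. The exact interval is so wide at these sizes that the main damage is the shift in the rate and limits, not loss of coverage.

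**Dose decision.** Section 2.3.4 treats a level as exceeding the MTD when at least 2 patients have a DLT. This is a count and contains no denominator, so u does not enter it.

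**The case against.** The best counter-argument is that the SAP's general rules may already remove these patients. Section 3.1.2 bases percentages on patients with non-missing assessments, and Section 3.1.4 rules out imputation unless specified. If an unevaluable patient counts as having a missing DLT assessment, that patient leaves the denominator. Section 3.2.3 also shows that membership of the set does not settle every denominator, since it asks for a post-dose measurement before a laboratory or vital-sign parameter is analysed. And the dose cohort in Section 3.10.1 could be read as the cohort of 6 after replacement.

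This weakens the point but does not remove it. A DLT is an event. A patient who left early has no event recorded, and nothing in the SAP classes that as a missing assessment. The condition in Section 3.2.3 asks for one laboratory or vital-sign value, not for completion of a DLT window. The table title names the safety population, and a programmer following it would count all dosed patients.

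It is also fair to say that the DLT definition, the window and the meaning of unevaluable may be in the protocol, which is not shown. If so, the SAP still directs the rate to a different population. Listing 16.2.1.2, of patients not evaluable for efficacy or safety, already covers part of the reporting, but it is not tied to the DLT rate.

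Two stronger readings are tempting and are not supported. A reader might infer that the reported rate is biased low in all circumstances. It is not: dilution needs at least one replaced patient who was dosed, and with zero DLTs the point estimate does not move. A reader might also infer that the MTD or RP2D determination is compromised. The rule uses counts, and the SAP compares the rate with no threshold.

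**Conclusion.** The point holds in conditional form. The SAP names a population for the DLT rate that does not fit its own replacement rules, so this is a stated population to be corrected and not merely a silence to be filled. The number of dosed replacements decides whether it matters in practice. Over the assumed range of one to three per cohort of 6, the reported rate falls by 14%, 25% or 33% in relative terms (1 - 0.86, 1 - 0.75, 1 - 0.67). These sizes assume a full cohort of 6 evaluable patients and no counted DLT among those replaced. The SAP does not say that the end of Cycle 2 is also the end of the DLT window, so the two should not be equated without the protocol. What is at stake is the accuracy of a reported Phase 1b summary.

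**What to change.** Add a DLT-evaluable set to Section 3.2: Phase 1b patients who had a DLT, or who completed the protocol's DLT window without being replaced. Word it to agree with the replacement rules in Section 2.3.1 and with the window as the protocol defines it. State in Section 3.10.1 that the DLT rate and exact interval use this set, and relabel Table 14.4.1.1 to match. Keep the Safety Analysis Set for all other adverse event summaries. Listing 16.2.1.2 can identify the dosed patients who were replaced, so that the difference between the two sets is visible.

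The cost is one set definition, one sentence and one table label. It needs no new data and changes no dose rule.

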2.3 STUDY DESIGN

Study SNDX-275-0603 is a randomized, placebo-controlled, double-blind, multicenter Phase 1b/2 study evaluating the combination of entinostat with avelumab in patients with advanced epithelial ovarian cancer. The study has 2 phases: an open-label Safety Lead-in (Phase 1b) followed by an Expansion Phase (Phase 2) (Figure 2-1).

A cycle is defined as 14 days in length. During treatment, patients will attend study center visits for study evaluations on Days 1 and 8 of Cycles 1 and 2, and on Day 1 of each cycle thereafter. Patients will have radiological disease assessments performed within 28 days prior to enrollment, then every 6 weeks (\pm 3 days) when measured from Cycle 1, Day 1, during study treatment through Week 36 (i.e., Weeks 6, 12, 18, 24, 30, 36) until unequivocal PD per RECIST 1.1. Patients remaining on study after Week 36 will undergo radiological disease assessments every 8 weeks (\pm 3 days) until unequivocal PD occurs. Disease will be assessed by computed tomography (CT) and magnetic resonance imaging (MRI), as appropriate, using the same method used for the screening evaluation, and response will be assessed by the investigator using RECIST 1.1 and irRECIST. Collection of fresh tumor tissue core biopsy (image-guided if applicable) and blood samples are outlined in Section 6.1 of the protocol.

Figure 2-1. Study Schema

Patients will remain on study treatment until unequivocal PD, intolerable toxicity, or one of the other study withdrawal criteria is met (see Protocol Section 11). Patients

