The Expansion Phase will evaluate the efficacy and safety of entinostat (compared to placebo) when administered at the recommended Phase 2 dose with avelumab in a randomized, double-blind, placebo-controlled setting. Progression-free survival will be the primary measure of efficacy; secondary measures of efficacy include ORR, CBR, DOR, TTR, and OS. Up to 120 patients with advanced epithelial ovarian cancer will be randomized to receive avelumab with entinostat or placebo in a 2:1 allocation. The randomization will be stratified by the presence of bulky disease (defined as a tumor ≥ 50 mm) versus not and by a history of progression while on primary platinum treatment or within 1 month from completion of primary platinum-containing regimen versus not.

The sample size was based on the following considerations. The true median PFS for patients with advanced epithelial ovarian cancer receiving avelumab monotherapy is expected to be approximately 3 to 4 months when measured from randomization. It is

hypothesized that the combination of entinostat and avelumab will reduce the hazard of disease progression or death without documented disease progression beforehand by 43% (i.e., true hazard ratio [HR] of 0.57). Under the exponential distribution, such a reduction in the hazard rate represents a 75% improvement in true median PFS relative to that of the control arm. If true median PFS is 3 months for patients receiving avelumab monotherapy, then true median PFS will be improved by approximately 2.25 months (i.e., 3 vs 5.25 months). Similarly, if true median PFS is 4 months for the control arm, then true median PFS will be improved by 3.0 months (i.e., 4 vs 7 months).

The primary analysis of PFS will be performed using a stratified log-rank test, stratifying on the randomization stratification factor(s). Total information of 97 PFS failures, defined as documented PD by RECIST 1.1 or death due to any cause without prior documented PD, is estimated to provide 90% power to detect the aforementioned 43% reduction in the PFS failure HR with 1-sided significance level of 0.10 (SEQDESIGN procedure, SAS version 9.4).

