3.7 Treatment Exposure

The overall duration of study drug administration (in days) and the total number of cycles started will be tabulated for each patient and summarized for each study phase. The average dose administered and cumulative dose of entinostat administered (in mg)

will be calculated. These data will be further summarized by calculating the mean, standard deviation, median, and range of these values. The average proportion of the planned doses of study drug will be calculated for all patients. Similar analyses will be performed for avelumab administration (in mg/kg). The number and proportion of patients with one or more dosage modification (i.e., reduction or delay) of each study drug will be tabulated along with the reasons for dosage modification. The primary reason for study drug discontinuation will be tabulated in a similar manner. All treatment exposure data will be presented in patient listings for the Safety Analysis Set.

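### Phase 2 adverse events are summarised only as crude incidences by arm, which mixes toxicity with a time at risk that the design expects to be longer on entinostat

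*SAP*

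**What the plan says.** Section 3.10.1 fixes the AE measure: "Incidences of all AEs will be presented by SOC and PT by dose cohort in Phase 1 and by treatment arm in Phase 2". Serious, Grade 3 or greater, related, fatal, dose-modification and discontinuation AEs are handled in the same way. The AE tables listed in Section 6.1 (the 14.4.1 to 14.4.7 series) match this. None gives a rate per patient-time, a time to first event, a cumulative incidence, or a split by cycle or fixed window.

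The definition of treatment emergence has a start but no stated end: "Treatment-emergent AEs are defined as having onset after study drug dosing or a sign, symptom, or diagnosis that worsens after study drug dosing".

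Treatment length depends on outcome. Section 2.3 says "Patients will remain on study treatment until unequivocal PD, intolerable toxicity, or one of the other study withdrawal criteria is met". Section 2.3.1 assumes a hazard ratio of 0.57 and says that "such a reduction in the hazard rate represents a 75% improvement in true median PFS relative to that of the control arm", giving medians of 3 against 5.25 months or 4 against 7 months.

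Section 3.7 and Tables 14.3.1.1 and 14.3.1.2 summarise exposure, but nothing links it to the AE tables. Section 3.8 places the main safety analysis at the primary PFS cutoff.

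**The concern.** The proportion of patients with an event depends on how often the event occurs and on how long patients are watched for it. When treatment ends at progression and one arm is expected to progress later, that arm has longer to accumulate events. Two arms with the same monthly risk can then show different crude incidences.

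Safety and tolerability of the combination is a stated secondary objective (Section 2.1.2), and avelumab plus placebo is the only control for what entinostat adds. If the PFS gain appears, the tables will tend to overstate the added toxicity. If patients leave entinostat early, they may understate it. The planned tables do not let a reader separate these effects, because patient-time to first event cannot be recovered from separate aggregate summaries of AEs and exposure.

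**Working it through.** **Plan's own figure.** 1/0.57 = 1.754, so a 43% hazard reduction does correspond to a median about 75% longer under the exponential model: 3 × 1.75 = 5.25 and 4 × 1.75 = 7.

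**Inputs from the SAP.** Medians 4 and 7 months; 12 months of accrual plus 12 of follow-up (Section 2.3.1).

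**Assumptions, not in the SAP.** Time on treatment T follows PFS and is exponential with rate μ = ln 2/median, i.e. 0.1733 (control) and 0.0990 (entinostat) per month. Both arms share one constant AE hazard λ. Accrual is uniform, so potential follow-up C is uniform from 12 to 24 months. AEs count for W months after treatment ends, with W = 0 or 3.

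**Step 1: time at risk.** Averaging min(T + W, C) over C gives

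W + 1/μ − (1/μ²) × [exp(−μ(12 − W)) − exp(−μ(24 − W))]/12.

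- W = 0, control: 5.771 − 33.30 × (0.1250 − 0.0156)/12 = 5.47 months.
- W = 0, entinostat: 10.099 − 101.99 × (0.3048 − 0.0929)/12 = 8.30 months. Ratio 1.52.
- W = 3, control: 3 + 5.771 − 33.30 × (0.2102 − 0.0263)/12 = 8.26 months.
- W = 3, entinostat: 3 + 10.099 − 101.99 × (0.4102 − 0.1250)/12 = 10.68 months. Ratio 1.29.
- Unlimited follow-up, W = 0: 10.10/5.77 = 1.75.

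**Step 2: crude incidence.** For given C it is

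1 − exp(−λW) × {1 − [λ/(λ + μ)] × [1 − exp(−(λ + μ)(C − W))]},

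averaged over C. With λ = 0.05 per month:

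| Follow-up and window | Control | Entinostat | Ratio |
|---|---|---|---|
| 12 + 12 months, W = 0 | 21.9% | 30.9% | 1.42 |
| 12 + 12 months, W = 3 | 32.3% | 39.3% | 1.22 |
| Unlimited, W = 0 | 22.4% | 33.6% | 1.50 |

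For example, the first control entry is 0.2239 × (1 − 0.0238) = 0.219, where 0.2239 = 0.05/(0.05 + 0.1733) and 0.0238 is the mean of exp(−0.2233 C). The true rate difference is zero in every row.

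**Step 3: other hazards.** On the 12 + 12 month timeline, λ = 0.02 gives 9.9% against 14.7% (W = 0) and 14.9% against 18.8% (W = 3). λ = 0.10 gives 36.2% against 48.5% and 52.3% against 60.8%. The gap therefore runs from about 4 to 12 points.

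**Step 4: early-onset events.** If the hazard acts only in the first 2 months, incidence is [λ/(λ + μ)] × [1 − exp(−2(λ + μ))]. With the SAP's two pairs of medians, a control incidence of 10% becomes 10.7% to 11.0%, 30% becomes 32.0% to 32.7%, and 50% becomes 53.1% to 54.1%. The gap is about 1 to 4 points.

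**Step 5: reversal.** If entinostat patients stopped early enough to have a median time on treatment of 3 months (assumed) against 4 on control, the Step 2 formula with λ = 0.05 and W = 0 gives 17.6% on entinostat against 21.9% on control.

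**The case against.** The strongest reply is that nothing here is an internal contradiction. Crude incidence by arm is a legitimate description, the table list agrees with the text, no AE test or between-arm interval is planned, and exposure is reported by arm, so an imbalance would be visible. All of that stands. It limits the point to interpretation and makes it a supplement, not a correction. It does not remove the point, because a visible imbalance is still not adjusted for.

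Three stronger readings are tempting and are not supported.

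- A reader might infer that time at risk would be 1.75 times longer on entinostat. That holds only with unlimited follow-up and no counting after treatment ends. The SAP's timeline caps follow-up, and its open-ended treatment-emergence definition, with safety visits to 90 days after the End of Treatment visit (Section 2.3), suggests that some post-dose time may count. The actual collection window may be set in the protocol.
- A reader might infer that all Phase 2 safety analyses share the weakness. They do not: Section 3.10.2 summarises laboratory values and changes, Section 3.10.3 follows vital signs over time, and Tables 14.4.10.1 and 14.4.10.2 give laboratory grades by cycle.
- A reader might infer that the tables must exaggerate entinostat toxicity. The direction depends on whether the PFS gain occurs and on how long patients stay on treatment, which may outlast RECIST 1.1 progression (Sections 2.3 and 2.3.6) or end sooner for toxicity.

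It is also fair to object that dividing by exposure assumes a constant rate and can dilute toxicity that arises early. That is why a rate alone is not enough.

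**Conclusion.** The concern holds for Phase 2 AE summaries only, as a low-cost improvement. As planned, AE incidence is confounded with time at risk in a design whose own hypothesis implies unequal time at risk. With 4 and 7 month medians, equal constant hazards and the 12 + 12 month timeline, time at risk is about 1.3 to 1.5 times longer on entinostat. At 0.05 per month the spurious gap is about 9 points with no post-dose window and 7 with a 3-month window.

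These sizes rest on time on treatment following PFS and on hazards and windows that the SAP does not give. No type I error rate, sample size or efficacy conclusion is affected.

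**What to change.** In Section 3.10.1 keep the crude tables. For all TEAEs, Grade 3 or greater, serious, and discontinuation AEs, add by arm:

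1. First-event exposure-adjusted incidence rates (patients with a first event divided by patient-months at risk up to that event or the end of the window), with the rate difference. State one at-risk window, defined identically for both arms, including when it closes after the last dose.
2. Cumulative incidence to a fixed early time such as Week 12, by an estimator that censors at the end of follow-up and treats death as a competing event. State whether stopping treatment ends time at risk. This guards against the dilution of early toxicity in item 1.

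Add the matching tables to Section 6.1. The data (AE dates, dosing dates, death and cutoff dates) are already needed for the planned analyses. The cost is a few extra tables and the constant-rate assumption in item 1, which should be stated in the table footnote.
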